APPENDIX C: Data Collection Forms

Village Questionnaire

Cov	erage Survey - Village Questionnaire To be answered by the	ne interviewee
1	Date (DD/MM/YYYY)	
2	Interviewer Name	
3	GPS South on Arrival	
4	GPS East on Arrival	
5	District name (of implementation unit)	
6	TA name	
7	Village name	
8	What is the position in the village of the person being interviewed? (ENTER CODE)	
9	What is the total population of the village?	
10	What is the number of households in the village (interviewee to estimate if not known)	
11	Source of population data? (ENTER CODE)	
12	When was the mass treatment for schistosomiasis carried out? (month/year)	
13	How was the mass treatment provided in the village? (ENTER CODE)	
14	Did this treatment include adults?	□ Yes □ No
15	If the treatment was community based, how was treatment in the village carried out? (ENTER CODE)	
	To be answered by the interviewer	
16	Method of random sampling of households	Random selection from household listBottle spinning method
17	Notes about village interview	

8. Interviewee position?	11. Source of population data	13 How was the MDA
1. Village chief	1. Village register	treatment provided in the
2. Village deputy chief	2. Election register	village??
3. School head teacher	3. LF register	1. No MDA treatment was
	4. Malaria register	carried out
	5. Onchocerciasis register	2. School-based treatment
	6. General health register	3. Community-based
	7. Other (please specify)	treatment
		4. Both school-based and
		community-based
		treatment
		5. Do not know
15. If treatment was		
community based, how was		
treatment in the village		
carried out?		
1. Door to door		
2. At the house of the village		
head		
3. Central point in the village		
4. Local health centre		
5. At the village school		
6. Other		
7. Do not know		

Household Questionnaire

	Coverage Survey – Household Form To be an	nswered by the interviewer
7	What number house is this for you in the village?	
	(Enter one number)	
8a	Was this house interviewed?	D No
	(Tick one box)	Yes on first visit
		Yes on second visit
8b	If household not interviewed: Reason why	
	household not interviewed	
	(Tick one box)	
		Household not found or destroyed
		L Other
8c	If household not interviewed and reason 'other'	
	Reason not interviewed: other	
0	(Enter reason)	
9	Consent form signed by Head of House?	No: stop interview
	(Tick one box)	L Yes
	To be answered by the interviewee Household head	d or other adult
10	How many people live in this household?	
	(Enter one number)	
11	How many adult males live in this house (15 or	
	(Enter one number)	
12	How many adult females live in this house (15 or	
	older)?	
	(Enter one number)	
13	How many boys live in this house (5-14 years	
	old)?	
1/	(Enter one number)	
14	(Enter one number)	
15	Notes about household interview	
	Answered by interviewer	
Equ	ity Questionnaire — To be answered by the househ	old head or other adult interviewee
E1. (Does your household have mobile telephone?] Yes
(Tick	one box)	
E2. [Does your household have a television?	
(Tick	one box)	
		_ No

E3. Does your household have electricity ?	The Yes
	□ No
E4. Does your household have a radio?	T Yes
	□ No
E5. Does your household have a telephone(landline)?	The Yes
(Tick one box)	□ No
E6. Does your household have a refrigerator?	The Yes
	□ No
E7. Does any member of your household own a	T Yes
bicycle? (Tick one box)	
E8. Does any member of your household own a	The Yes
motorcycle or motor scooter? (Tick one box)	D No
E9. Does any member of your household own a car	T Yes
or truck? (Tick one box)	D No
E10. Does any member of this household have a bank	T Yes
E11. What is the main source of drinking water for	Piped into dwelling
(Tick one box)	Piped into yard/plot
	Public tap / standpipe
	Tube well or borehole
	Unprotected dug well
	Unprotected Spring
	Surface water-river, lake, dam, pond
	Other
E12. What kind of toilet facility do members of your	Flush or pour flush toilet
(Tick one box)	Ventilated Pit Latrine (VIP) latrine
	Pit latrine without slab / open pit
	Pit latrine with slab
	□ No facility/bush/field
	Other
E13. Do you share this toilet facility with other	Yes
E14. What type of fuel does your household mainly	Electricity
(Tick one box)	Wood
	Charcoal

	□ Other
E15. What is the main material of the floor in your	Cement
household?	Ceramic Tile
	Earth, Sand, Dung
	☐ Other
E16. What is the main material of the exterior walls	Stone walls with lime/cement
In your household? (Tick one hox)	Unburnt bricks
	Cane/pal/trunks/dirt
	Bamboo/tree trunks with mud
	Cement Cement
	Burnt bricks
	☐ Other
E17. What is the main material of the roof in your	Thatch/palm leaf
household? (Tick one hox)	Pal/Bamboo/grass
	🗖 Iron Sheet
	□ Other

Individual Questionnaire

English Questions	Participant
Name of person randomly selected? (Enter name)	
Was this person interviewed?	☐ Yes
(Tick one box)	□ No
If person not interviewed:	Absent during survey
Reason for no interview?	Refused to participate
(Tick one box)	Other
If person not interviewed and reason no	
Interview 'other': Other reason no interviewed?	
(Enter reason)	
Interview start time (HH.MM)	
Is this person being interviewed	☐ Yes
confidentially?	
Consent received?	
	L No
Participant age? (Enter one number)	
Sex (M/F)? (Tick one box)	
	L Female
What is your occupation?	
(ENTER CODE)	
Adults only, if occupation is other:	
(write answer)	
Adult female only:	
Were you pregnant or breastfeeding in July	
2017? Children only:	
Have you attended school in the last school	
year: January 2017 to December 2017?	LJ No
(Tick one box)	
If attended school in last school year: What type of school do you attend?	
(ENTER CODE)	
How did you hear about the mass	
treatment? (ENTER CODE)	

English Questions	Participant
If heard about mass treatment is other:	
How did you hear about the mass treatment	
- other : (write answer)	
Individual knowledge of the schistosomiasis	
mass treatment	
show particpants props and (tick all objects	
recognised, or 'none' if don't recognise any)	Dose pole
	□ None of above
Did you swallow PZQ at the mass treatment?	The Yes
(show dose pole/tablets)	
(Tick one box)	
If did not swallow PZQ:	
Reasons for not swallowing PZQ	
If did not swallow PZQ, and other reason for	
not swallowing PZQ:	
Other reasons for not swallowing PZQ	
(write answer)	
IJ Swallowed P2Q: Where did you take the P7O?	
(ENTER CODE)	
Did you swallow ALB at the mass treatment	Tes Yes
(show tablet)?	
(Tick one box)	
If did not swallow ALB:	
Reasons for not swallowing ALB	
If did not swallow ALB. and other reason for	
not swallowing ALB:	
Other reasons for not swallowing ALB	
(write answer)	
If swallowed ALB: Where did you take the ALB?	
(ENTER CODE)	
If swallowed PZQ or ALB:	
How did you take the PZQ and ALB tablets?	
If swallowed PZQ or ALB:	
swallowed the tablets?	
(Tick one box)	LJ No

English Questions	Participant
If swallowed PZQ or ALB/MEB: Had you eaten in the two hours before you took the tablets? (Tick one box)	☐ Yes ☐ No
Who decided whether you took the treatment or not? (ENTER CODE)	
If who decided is other: Who decided whether you took the treatment or not - other? (write answer)	
Did you know beforehand when and where the MDA would take place? (ENTER CODE)	
How far was the distribution point from your	
What is the language you use to communicate at home?	 Chewa / Nyanja Yao Lomwe Nkhonde Ngoni Tumbuka Sena Nyakusa Tonga Lambya Senga Sukwa Other
How frequently do you listen to the radio during a week? READ OPTIONS	 More than once a day At least once a day 2 or 3 times per week Once a week Never
[IF AT LEAST ONCE A WEEK] What radio station do you most commonly listen to? WRITE ANSWER	 Zodiak Station MBC Radio Dzimwe Community Radio Nkhota–Kota Radio Neno Community Radio Mzati Community Radio Dziko Community Radio

English Questions	Participant
	🗖 Mzimba Radio
	Dinosaur Community Radio
	Other
What other radio stations do you listen to?	Zodiak Station
MENTIONED AND STATE OTHERS	MBC Radio
	Dzimwe Community Radio
	Nkhota–Kota Radio
	Neno Community Radio
	Mzati Community Radio
	Dziko Community Radio
	🗖 Mzimba Radio
	Dinosaur Community Radio
	Other
The proceeding questions are played with	
radioclips (10seconds in length) in the	
During June and July 2017, the Ministry of	
Health broadcasted a series of radio shows	
schistosomiasis I will now ask you a few	
questions about these broadcastings.	
During that time, do you recall having listed to	T Yes
this radio clip: [PLAY CLIP 1: Mother	
testimonial]?	
[IF YES] Can you tell us what you recall was	A Mother describes a conversation with a doctor
TICK ALL ELEMENTS RESPONDENT IDENTIFIES	Malawi's children have SCH
AS PART OF CLIP	SCH affect mental and physical health
	SCH may show no symptoms
	Children need treatment (medicine) every year
	Distribution is for free
	Children who don't attend school can receive treatment
	Children need to eat prior to MDA.
During that time, do you recall having listed to	The second secon
this radio clip: [PLAY CLIP 2: Doctor testimonial]?	□ No
[IF YES] Can you tell us what you recall was mentioned in this radio clip?	A doctor talks to the audience about SCH
TICK ALL ELEMENTS RESPONDENT IDENTIFIES	Malawi's children have SCH
AS PART OF CLIP	SCH affect mental and physical health
	SCH may show no symptoms

English Questions	Participant
	Children need treatment (medicine) every year
	Distribution is for free
	Children who don't attend school can receive treatment
	Children need to eat prior to MDA.
During that time, do you recall having listed to	T Yes
this radio clip: [PLAY CLIP 3: Give me my broakfast]?	□ No
IF RECALLED FITHER CLIP 1, 2 OR 31 Did you	
discuss the content of any of those clips with	Yes
your family, friends or neighbours?	L No
[IF YES] What topics did you discuss with them?	MDA dates
TICK ALL TOPICS MENTIONED	Malawi's children have SCH
	SCH affect mental and physical health
	SCH may show no symptoms
	Children need treatment (medicine) every year
	Distribution is for free
	Children who don't attend school can receive treatment
	Children need to eat prior to MDA.
	Other (specify)
Apart from the clips we played to you, did you	T Yes
lune and July 2017 about MDAs against [LOCA]	□ No
TERM FOR SCH]?	
[IF YES] What information was provided in these	MDA dates
radio programmes?	Malawi's children have SCH
	SCH affect mental and physical health
	SCH may show no symptoms
	Children need treatment (medicine) every year
	Distribution is for free
	Children who don't attend school can receive treatment
	Children need to eat prior to MDA.
	Uther (specify)

Individual Answer Code

Answer codes for Household an	d Individual questions
23a: What is your occupation?	24b: What type of school do you attend?
1. Farmer	1. Primary (public or private)
2. Merchant	2. Secondary (public or private)
3. Health worker	3. Religious school
4. Housewife	
5. Student	
6. Fisherman	
7. Medicines distributor	
8. Teacher	
9. Village Head	
10. Does not work	
11. Other (please specify)	
25a. How did you hear about the drug	27b: Reasons for not swallowing PZQ
distribution?	28b: Reasons for not swallowing ALB/MEB
1. Teacher	1. Too young
2. Village Meeting	2. Too old
3. Posters / flyers	3. Pregnant
4. Health professional	4. Breast feeding
5. Newspaper	5. Too sick
6. Radio	6. Feels healthy
7. TV	7. Fear of side effects
8. Town crier (loud speaker)	8. Bad smell or taste
9. Place of worship	9. Tablets are too large
10. Banner	10. Rumours
11. Other (please specify)	11. Does not know
	12. Drugs ran out
	13. Was at work
	14. Not living in the village at time of MDA
	15. Absent from school on day of MDA
	16. Does not attend school
	17. There was no MDA
	18. Had not heard about MDA
	19. Too far from distribution point
	20. Refused to answer
	21. Was not invited to MDA
	22. Had not eaten before MDA
	23. Too many tablets
	24. Medicine does not work
	25. Other (please specify)

27d: Where did you take PZQ?	29: How did you take the PZQ and ALB tablets?
28d: Where did you take ALB?	1. All at the same time
1. School	2. I took them all throughout the day but not all at
2. Home (door-to-door)	the same time
3. House of the village head	3. I took them all but not on the same day
4. Central point in the village	4. One tablet a day until they were all finished
5. Local Health Centre	5. I took some but not all of them
6. District Clinic	6. I was given the tablets but did not swallow them
7. Other	7. Do not remember
8. Does not know	
32: Who decided whether you took the	e 33: Did you know beforehand when and where the
treatment or not?	MDA would take place?
1. Me	1. Did not know when or where
2. Father	2. Knew when only
3. Mother	3. Knew where only
4. Other family member	4. Knew when and where
5. School teacher	
6. Village Head	
7. Traditional Healer	
8. Health worker or drug distributor	
9. Other (please specify)	
10. Did not know about the distribution	
34: How far was the distribution point	
from your home if walking?	-
1.0 - at home or in school	
2. Less than 30 minutes	
3. 30 to 60 minutes	
4. 1 to 2 hours	
5. More than 2 hours	
6. Do not know	

Translated Survey

English	Chichewa
Village Questions	
What is the total population of the village?	Kodi muli ndi anthu ochuluka bwanji mmudzi muno
What is the number of households in the village (interviewee to estimate if not known)	Muli mabanja angati mmudzi muno
Source of population data?	Munagwilitsa njira yanji kuti mupeze chiwerengero chimenechi
When was the mass treatment for schistosomiasis carried out?	Mankhwala a Likodzo anagawidwa liti mmudzi muno
Where was the mass treatment provided in the village?	Kodi mankhwalawa amagawidwa kuti
Did this treatment include adults? (should be swapped with question 15)	Kodi aakulu amalandila nawo
If the treatment was community based, how was treatment in the village carried out?	Ngati anaperekedwa kumudzi, ndi njira yanji anasata
Household Questions	
Does your household have mobile telephone?	Muli ndi foni ya mmanja
Does your household have a television?	Muli ndi kanema/TV
Does your household have electricity ?	Kodi nyumbayi ili ndi magetsi
Does your household have a radio?	Muli ndi wayilesi
Does your household have a telephone(landline)?	Kodi muli ndi foni ya chingwe/mnyumba
Does your household have a refrigerator?	Muli ndi filiji
Does any member of your household own a bicycle?	Alipo amene ali ndi njinga ya kapalasa mnyumba muno
Does any member of your household own a motorcycle or motor scooter?	Alipo amene ali ndi njinga ya moto nyumba muno
Does any member of your household own a car or truck?	Alipo amene ali ndi galimoto yaying'ono kapena lore mnyumba muno

English	Chichewa
Does any member of this household have a bank account?	Alipo amene ali ndi bukhu la ku banki mnyumba muno
What is the main source of drinking water for members of your household?	Mumatunga kuti madzi akumwa
What kind of toilet facility do members of your household usually use?	Chimbudzi chanu nchotani
Do you share this toilet facility with other households?	Chimbudzichi Mumagwiritsa ntchito ndi mabanja ena
What type of fuel does your household mainly use for cooking?	Mumaphikila pachani nthawi zones
What is the main material of the floor in your household?	Pansi panyumba yanu mpotani
What is the main material of the exterior walls in your household?	khoma la nyumba yanu mudamangila chani
What is the main material of the roof in your household?	Nyumba yanu munafolela ndichani
Individual Questions	
English Questions	Chechewa Translation
English Questions Name of person randomly selected? (Enter name)	Chechewa Translation
English Questions Name of person randomly selected? (Enter name) Was this person interviewed? (Tick one box)	Chechewa Translation
English Questions Name of person randomly selected? (Enter name) Was this person interviewed? (Tick one box) If person not interviewed: Reason for no interview? (Tick one box)	Chechewa Translation
English Questions Name of person randomly selected? (Enter name) Was this person interviewed? (Tick one box) If person not interviewed: Reason for no interview? (Tick one box) If person not interviewed and reason no interview 'other': Other reason no interviewed? (Enter reason)	Chechewa Translation
English Questions Name of person randomly selected? (Enter name) Was this person interviewed? (Tick one box) If person not interviewed: Reason for no interviewed: (Tick one box) If person not interviewed and reason no interview 'other': Other reason no interviewed? (Enter reason) Interview start time (HH.MM)	Chechewa Translation
English Questions Name of person randomly selected? (Enter name) Was this person interviewed? (Tick one box) If person not interviewed: Reason for no interview? (Tick one box) If person not interviewed and reason no interview 'other': Other reason no interviewed? (Enter reason) Interview start time (HH.MM) Is this person being interviewed confidentially? (Tick one box)	Chechewa Translation
English Questions Name of person randomly selected? (Enter name) Was this person interviewed? (Tick one box) If person not interviewed: Reason for no interview? (Tick one box) If person not interviewed and reason no interview 'other': Other reason no interviewed? (Enter reason) Interview start time (HH.MM) Is this person being interviewed confidentially? (Tick one box) Consent received? (Tick one box)	Chechewa Translation

English	Chichewa
Sex (M/F)?	
(Tick one box)	
Adults only:	Mumagwira ntchito yanji
What is your occupation?	
(ENTER CODE)	
Adults only, if occupation is other:	
What is your occupation - other?	
(write answer)	
Adult female only:	
Were you pregnant or breastfeeding in July 2017?	
Children only:	Mumapita kusukulu telemu yathayi
Have you attended school in the last school year:	
January 2017 to December 2017?	
(Tick one box)	
If attended school in last school year:	Munali kalasi yanji telemu yathayi
What type of school do you attend?	
How did you hear about the mass treatment? (ENTER	Munamvera kuti/kwandani za ku gawa
CODE)	
If neuro about mass treatment is other.	
(write answer)	
Individual knowledge of the schistosomiasis mass	
treatment	
show participants props and (tick all objects	
recoanised, or 'none' if don't recoanise any)	
Did you swallow PZQ at the mass treatment? (show	Munamwera konko mankhwala a likodzo.
dose pole/tablets)	
(Tick one box)	
If did not swallow PZQ:	Ngati simunamwere konko, Chifukwa chani
Reasons for not swallowing PZQ	
(ENTER CODE)	
If did not swallow PZQ, and other reason for not	Zifukwa zina
swallowing PZQ:	
Other reasons for not swallowing PZQ	
(write answer)	
If swallowed PZQ:	Munamwera kuti mankhwala a likodzo
Where did you take the PZQ?	
(ENTER CODE)	
Did you swallow ALB at the mass treatment (show	i Wiunamwera konko mankhwala a njoka za
(Tick one box)	mmimba.
If did not swallow ALP:	Chifukwa chani simunamwara nanma
I ulu Hol Swallow ALD. Reasons for not swallowing ALR	mankhwala a nicka za mmimba
(ENTER CODE)	

English	Chichewa
If did not swallow ALB, and other reason for not	Pali zifukwa zina
swallowing ALB:	
Other reasons for not swallowing ALB	
(write answer)	
If swallowed ALB:	Munamwera kuti mankhwala a njoka za
Where did you take the ALB ?	mmimba
(ENTER CODE)	
If swallowed PZQ or ALB:	Munamwa motani
How did you take the PZQ and ALB tablets?	
(ENTER CODE)	
If swallowed PZQ or ALB:	Ogawa mankhwala ankakuonani mukumwa
Was the distributor present when you swallowed the	mankhwala
tablets?	
(TICK ONE DOX)	
If swallowed PZQ or ALB/MEB:	Muhali mutadya musahamwe mahkhwala
Had you eaten in the two nours before you took the	
(Tick one hex)	
(TICK OTTE DOX)	Anakunangila chiganizo ndani kuti mumuo
not2	kanona musamwa mankhwala
If who decided is other:	
Who decided whether you took the treatment or not	
- other?	
(write answer)	
Did you know beforehand when and where the MDA	Kodi munali mukudziwa kale za
would take place?	nthawi/masiku ndi malo omwera
(ENTER CODE)	mankhwala a likodzo
How far was the distribution point from your home if	Munayenda nthawi yochuluka bwanji
walking? (ENTER CODE)	kukafika komwe amagawila mankhwala
What is the language you use to communicate at	Mumayankhula chiyankhulo chanji
home?	
How frequently do you listen to the radio during a	Mumamvera ka ngati wayilesi pa
week?	sabata/mulungu
READ OPTIONS	
[IF AT LEAST ONCE A WEEK] What radio station do	Mumakonda kumvera wayilesi yanji
you most commonly listen to?	
WRITE ANSWER	
What other radio stations do you listen to?	Mumakonda kumvera wayilesi imodzi mwa
READ OPTIONS. TICK ALL STATIONS MENTIONED	IZI
AND STATE OTHERS	
The proceeding questions are played with radioclips	
(10seconds in length) in the relevant language	

English	Chichewa
During June and July 2017, the Ministry of Health broadcasted a series of radio shows to inform residents about MDA against schistosomiasis. I will now ask you a few questions about these broadcastings.	Mwezi wa juni ndi julayi chaka chino a unduna wa za umoyo analengezesa za kupereka kwa mankhwala a likodzo. Ndikufunsani mafunso angapo pa zomwe zinalengezedwazo
During that time, do you recall having listed to this radio clip: [PLAY CLIP 1: Mother testimonial]?	Mukumbukila kuti mudamverapo uthengawu
[IF YES] Can you tell us what you recall was mentioned in this radio clip? TICK ALL ELEMENTS RESPONDENT IDENTIFIES AS PART OF CLIP	Tandiuzeni kuti mukukumbukilapo chani pa uthenga mwamverawu
During that time, do you recall having listed to this radio clip: [PLAY CLIP 2: Doctor testimonial]?	Mukumbukila kuti mudamverapo uthengawu
[IF YES] Can you tell us what you recall was mentioned in this radio clip? TICK ALL ELEMENTS RESPONDENT IDENTIFIES AS PART OF CLIP	Tandiuzeni kuti mukukumbukilapo chani pa uthenga mwamverawu
During that time, do you recall having listed to this radio clip: [PLAY CLIP 3: Give me my breakfast]?	Mukumbukila kuti mudamverapo uthengawu
[IF RECALLED EITHER CLIP 1, 2 OR 3] Did you discuss the content of any of those clips with your family, friends or neighbours?	Munakambilanapo za uthengawu ndi wina aliyense
[IF YES] What topics did you discuss with them? TICK ALL TOPICS MENTIONED	Munakambilana mitu yanji
Apart from the clips we played to you, did you listen to any other radio broadcastings between June and July 2017 about MDAs against [LOCAL TERM FOR SCH]?	kupatula uthenga mwamverawu munamveraponso uthenga wina pa wayilesi okhuzana ndi kupereka mankhwala a likodzo chaka chino
[IF YES] What information was provided in these radio programmes? TICK ALL ELEMENTS MENTIONED	Uthenga wake unali woti chani

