In order to monitor and support NTD programme performance, independent drug *coverage surveys* are recommended by the WHO (WHO 2006). These coverage surveys should be carried out across all areas given PC, particularly at crucial time points during the programmes i.e. in the first year of the programme, in cases where coverage might be suspiciously high or low, to ensure any corrective actions where needed. In areas where routinely reported coverage is low, additional methods i.e. Key Informant Interviews and Focus Group Discussion are recommended to assess the causes of low coverage (WHO, 2005; WHO, 2010).

SCI currently uses cluster-sample surveys similar to those widely used by the Expanded Programme in Immunisation (EPI) and in other NTD programmes (WHO 1991; WHO 2005; Worrell and Mathieu 2012; Cromwell *et. al.* 2013; Baker *et. al.* 2013). The accuracy of routinely reported coverage estimates can be assessed by comparing these with survey-derived coverage estimates and their 95% confidence intervals. In addition to identifying over and under-reporting, in routinely collected data, these coverage surveys also provide data to assess other issues such as, MDA delivery strategies, biases in treatment coverage for example by gender, school enrolment, and examination of possible reasons for coverage failure. This information assists in the identification for recommended actions to improve programme delivery.

Schistosomiasis and STH in Malawi

Intestinal and urogenital schistosomiasis caused by infection with *S. mansoni* and *S. haematobium* is a widespread public health problem in Malawi. The Malawian Ministry of Health (MoH) has an ongoing national scale treatment programme for schistosomiasis control. All 29 districts are at varying stages of programme implementation. All districts are endemic for *Schistosoma mansoni* and *S. haematobium* and have received five or more rounds of annual treatment with praziquantel (PZQ) and albendazole (ALB) for Soil Transmitted Helminths (STH) since 2009 (MoH report). The mean prevalence of *S. mansoni* has reduced from 2.23% eggs per gram (epg) at baseline to 0.82% epg at the third follow up. With the prevalence of heavy infection reducing from 0.19% to 0. The prevalence of *S. haematobium* has also reduced from 9.21% at baseline to 3.64% at follow up three. Prevalence of heavy infection has reduced from 1.60% at baseline to 0.73% at baseline and mean intensity of infection (eggs/10ml) has reduced from 3.59 to 1.12.

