
Previous mapping

Prior to SCI working with the MoH in 2011 baseline mapping surveys had been conducted in a number of the districts between 2003 and 2010 to enable the national program to commence mass treatment campaigns. The first mapping exercise was carried out in Malawi in 2003 to determine the distribution of infection and help guide planned control through treatment. The surveys that were conducted focused on urine filtration to detect S. *haematobium* and found there was a significant burden of disease in all targeted districts. Results indicated both a widespread occurrence of infection, and a marked variability in infection prevalence. However, information relating to *S. mansoni* and STH infection was not gathered. Since the baseline mapping in 2003, 26 out of 28 districts have been mapped. Mapping results presented between 2003 and 2010 have varying protocols and results are taken straight from MoH unpublished reports¹.

Treatment History

Due to the willingness of the MoH, financial support from SCI and availability of purchased and donated PZQ and ALB, Malawi has conducted national treatment annually since 2012. This followed limited treatments which were distributed between 2009 - 2012 in several parts of the country.

All districts in Malawi have now received at least five rounds of treatment. From 2012 to date the target population within each district has expanded from targeting school-age children (SAC) through school treatments, to treating SAC through school and communities and some adults, to now conducting both school and community treatments targeting all SAC as well as adults in known high risk areas (which may sometimes be whole districts) based on previous mapping results. In 2014 districts were asked to begin categorising health centres, schools and villages into areas of high risk or not. This was based on either previous mapping results, abundance of water bodies or high risk agricultural activities i.e rice farming or fishing. Categorisation of high risk areas is based on local knowledge and practices of the areas and population.

¹ S:\SCI - post 3 June 2011\Current programmes\DFID\ICOSA\COUNTRIES\Malawi\Mapping\pre-ICOSA mapping\ Baseline Prevalence studies from [name]

Category	Prevalence	Action	
High-risk	≥50%	Treat all school-age children once a year	Simultaneously treat all adults once a year
Moderate-risk	≥10% but <50%	Treat all school-age children once a year	Also treat adults considered to be at risk

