APPENDIX A: Field team planning manual

Survey team composition

Include a brief description of the survey teams: The participants were identified by the Malawi program manager as people with skills and experience relevant for the activity. The backgrounds from the participants ranged from IT Graduates, retired teachers to experienced Nurses from within the MoH.

Survey teams will be made up of students and people known to the program with interview skills but had no part in the MDA.

There will be 6 teams made up of 1 team leader, 3 interviewers and a driver.

The survey will take 5 weeks to complete all districts working Monday – Saturday each week.

Survey team training

Training for the survey will be conducted by the SCI PM, MoH PM with additional input from other Program staff. Below are links to the various training materials that will be used. Each interviewer will be provided with an Interviewer manual and cheat sheet for using the phones.

The questionnaire will be translated prior to the training and will be reviewed during the training to ensure they are fully understood. Each team will be provided with the same dose pole that was used during each distribution (MDA), samples of each of the drugs that were provided, and examples of the posters and leaflets used during social mobilization. These will act as visual cues to the individuals in each HH.

Training Material

Agenda:

https://imperiallondon.sharepoint.com/sites/fom/SCI/The%20Hub/MWI_Coverage%20Survey%20Training% 20Agenda_OCT%202017.docx

Schisto Overview:

https://imperiallondon.sharepoint.com/sites/fom/SCI/The%20Hub/GLO_Schisto%20Program%20Overview% 20for%20Coverage%20Survey%20Training.pptx

Coverage Survey Overview:

https://imperiallondon.sharepoint.com/sites/fom/SCI/The%20Hub/GLO_PP_Coverage%20Survey%20Trainin g%20Template.pptx

Household Selection Exercise: https://imperiallondon.sharepoint.com/sites/fom/SCI/The%20Hub/MDG-%20HH%20selection%20exercise.pptx

Phone Use:

https://imperiallondon.sharepoint.com/sites/fom/SCI/The%20Hub/TOOL_Coverage_SurveyCTO_Cheat_She et_EN.docx

Practice Scenarios:

https://imperiallondon.sharepoint.com/sites/fom/SCI/The%20Hub/GLO_Coverage%20Survey%20Training%2 OPractice%20Household%20Scenarios_EN.docx

Coverage Manual:

https://imperiallondon.sharepoint.com/sites/fom/SCI/The%20Hub/MWI%20Interviewer%20Manual%20201 7.docx?d=w9fd6a56081c14123b115a778483f6a84&csf=1

Timetable of activities

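### The PZQ and ALB ingestion items do not name the July 2017 round, so some answers about earlier annual rounds can be counted in validated coverage

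*Protocol*

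**What the plan says.** Study Objectives defines validated coverage as the percentage of interviewed people who ingested the target drug. The numerator comes from two items in Appendix C, Individual Questionnaire: "Did you swallow PZQ at the mass treatment" and "Did you swallow ALB at the mass treatment". In the Translated Survey table they appear as "Munamwera konko mankhwala a likodzo" and, as extracted, "Wiunamwera konko mankhwala a njoka za", neither with a month or year.

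The round under evaluation ran from 10 to 14 July 2017 (Details of the MDA in Malawi 2017). Treatment History says that "Malawi has conducted national treatment annually since 2012" and that "All districts in Malawi have now received at least five rounds of treatment". The section on schistosomiasis and STH in Malawi confirms that the drugs were the same: districts "have received five or more rounds of annual treatment with praziquantel (PZQ) and albendazole (ALB").

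Timing of survey recognises recall bias, particularly where rounds are frequent. Its footnote 3 cites studies suggesting that recall may nevertheless be accurate in integrated campaigns.

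**The concern.** The survey must separate treatment in July 2017 from treatment with the same tablets in earlier years. If the count of at least five rounds includes 2017, at least four earlier ones remain. A respondent who was missed in July but treated before could answer yes with an earlier round in mind.

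The follow-up items ask where and how the tablets were taken, whether the distributor was present and whether the person had eaten. None asks when, so a wrong-round yes cannot be identified or removed in analysis.

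Such answers can only add to the numerator. They would favour the target of more than 75% (SO 1) and could mask over-reporting in the comparison with reported coverage (SO 2). The subgroup comparisons in SO 3 and SO 4 use the same items.

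**Working it through.** **1. The plan's own figure.** Appendix D gives p = 0.50, margin d = 0.09, ICC 0.1, 24 individuals per village and 95% confidence.
- n = z² p(1−p)/d² × [1 + (24 − 1) × 0.1] = 118.56 × 3.3 = 391.3, which matches the stated 391.
- 391.3 / 24 = 16.3, so 17 villages.

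The sample size is not in dispute. It supplies the yardstick of a 9-point margin.

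**2. Where a date or round cue appears.**
- Household introduction (Appendix B): refers to an activity in recent months. It is spoken to the household head or senior person present; individuals are then interviewed privately.
- Pregnancy/breastfeeding item: names July 2017 and comes before the ingestion items, but is for adult women only. Its Chichewa cell is blank as extracted.
- School attendance item: names January to December 2017 and comes before the ingestion items, but is for children only and concerns schooling. The Chichewa text shows no year.
- Radio block: names June and July 2017, but follows the ingestion items.
- Village form: asks the month and year of treatment, but of the village informant.
- Props: Appendix A says "Each team will be provided with the same dose pole that was used during each distribution (MDA"), so the pole does not identify one round. Drug samples and examples of the social mobilisation posters and leaflets are also shown.

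Adult men have no dated item before the ingestion questions. Adult women and children have one, on another subject.

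**3. Illustration of size.** The documents give no rate of wrong-round answers, so all inputs in this step are assumptions. Let c be true July 2017 coverage, s the share of missed people treated in an earlier round, and a the share of those who answer for that round. The upward component is (1 − c) × s × a.

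With c = 0.70 and s = 0.80:
- a = 0.10: 0.30 × 0.80 × 0.10 = 0.024, so 70% reads as 72.4%.
- a = 0.20: 0.30 × 0.80 × 0.20 = 0.048, so 70% reads as 74.8%.
- a = 0.30: 0.30 × 0.80 × 0.30 = 0.072, so 70% reads as 77.2%.

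With s halved to 0.40, the increments halve to 1.2, 2.4 and 3.6 points.

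**4. Thresholds.** Write f = s × a.
- True 70% reaches 75% when f = (0.75 − 0.70)/0.30 = 0.167. With s = 0.80 this needs a = 0.21.
- True 65% reaches 75% when f = 0.10/0.35 = 0.286.
- At true 50%, the component equals the 9-point margin when f = 0.09/0.50 = 0.18.

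**5. Offsetting error.** If a share g of people treated in July fail to report it, the net error is (1 − c)f − c·g. At c = 0.70 and f = 0.16 it is zero when g = 0.048/0.70 = 0.069. The net sign therefore depends on two rates that the documents do not give.

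**The case against.** The strongest reply is that the question is tied to one event.
- It refers to the mass treatment in the singular. It follows items on how the person heard of the mass treatment and on recognising its materials.
- Several reason codes presuppose a particular campaign, such as absence from school on the day.
- Both Chichewa ingestion items contain the word konko, while the items on where the drug was taken do not. The word may well carry the reference to the distribution.
- Training is compulsory and includes review of the translated questionnaire. The linked materials are not available, so interviewers may be told to state the round.
- Footnote 3 addresses recall directly.

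Most of this stands as mitigation. It makes the intended meaning clear to the survey team and probably to many respondents. It does not put a date into the question. Footnote 3 is hedged, and the Protocol does not say that it covers an undated question after several annual rounds.

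The objection to the size also stands. People missed in 2017 may be those missed before: the 2014 survey found coverage under 40% in non-attending children. Pre-school children were not a target group in 2017; if that also held earlier, the youngest school-age children had few or no earlier rounds. Either fact would make 80% too high for some groups.

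**Conclusion.** The point holds as a wording defect in the sole source of the coverage numerator. Neither ingestion item names the round, no cue dates it for every respondent, and no later item would reveal a wrong-round answer. That component of error is upward, is larger where true coverage is lower for a given f, and does not shrink with sample size. The 2.4 to 7.2 points are an illustration resting wholly on assumed values of c, s and a.

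A reader might infer more than the documents support:
- **That validated coverage will be too high overall.** Forgotten July doses act downwards, and Study Objectives counts missing ingestion answers as not taken. The net direction is not shown.
- **That a modest rate turns a missed target into a met one.** The middle case gives 74.8%, still short of more than 75% and within 9 points of the assumed true 70%.
- **That the household introduction is the only earlier time cue.** The July 2017 and 2017 school-year items precede the ingestion items for adult women and children.
- **That the Chichewa PZQ item makes no reference to the mass treatment.** No back-translation is given, and konko may supply that reference. Only the absence of a date is established.

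**What to change.** Add the words *in July this year (July 2017)* to "Did you swallow PZQ at the mass treatment" and "Did you swallow ALB at the mass treatment", and make the same change in the Chichewa versions. Before the treatment block, read each respondent one sentence saying that these questions concern only the July 2017 treatment.

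Any local event used as a memory aid should be confirmed at training. A cue based on the school holiday should not be used unless verified locally, because the documents do not give the 2017 holiday dates.

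The cost is the wording of two items in two languages, plus one spoken sentence per interview. The sample and the number of interviews do not change.
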